3.1.2.3 Season 1 or Season 2, CLD/CHD Cohort - Replacement Dose

Subjects in the CLD/CHD cohort who undergo cardiac surgery with cardiopulmonary bypass after receipt of Dose 1 but prior to receipt of Dose 5 will receive a replacement dose of the study drug that they received for Dose 1 immediately following the surgery when determined by the physician to be medically stable for an IM injection. Any subsequent doses of study drug will continue to be given according to the protocol-specified dosing schedule. In subjects requiring multiple surgeries during the same season, the dosing and timing scheme described below should be followed relative to the most recent replacement dose.

Details for the replacement dose by randomized group are presented below.

MEDI8897 Group

- Season 1
 - Subjects undergoing surgery < 90 days post first dose who originally received 50 mg MEDI8897 will receive a single 50-mg MEDI8897 IM replacement dose if < 5 kg body weight at time of replacement dosing or a single 100-mg MEDI8897 IM replacement dose if \geq 5 kg body weight at time of replacement dosing.
 - Subjects undergoing surgery < 90 days post first dose who originally received 100 mg MEDI8897 will receive a single 100-mg MEDI8897 IM replacement dose.
 - Subjects undergoing surgery \geq 90 days post first dose who originally received either 50 mg or 100 mg MEDI8897 will receive a single 50-mg MEDI8897 IM replacement dose.
- Season 2
 - Subjects undergoing surgery < 90 days post first dose will receive a single 200-mg MEDI8897 IM replacement dose.
 - Subjects undergoing surgery \geq 90 days post first dose will receive a single 100-mg MEDI8897 IM replacement dose.

Palivizumab Group

Subjects will receive a 15 mg/kg palivizumab IM replacement dose. Thereafter, doses should be given according to the protocol-specified dosing schedule.

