4.5.1.2 Dose Preparation Steps and Treatment Administration

The first day of dosing is considered Day 1.

Study drug (MEDI8897, placebo, and palivizumab) will be supplied by an unblinded investigational product manager. Blinding will be performed at the site level to ensure that MEDI8897, placebo, and palivizumab are indistinguishable in appearance and are not labeled to reveal treatment identity.

No incompatibilities between MEDI8897 or palivizumab and polycarbonate or polypropylene syringes have been observed.

MEDI8897 and palivizumab do not contain preservatives and any unused portion must be discarded. Total in-use storage time from needle puncture of the study drug vial to administration should not exceed 4 hours at room temperature. If storage time exceeds these limits, a new vial should be used.

MEDI8897 group: Season 1 and Season 2, including replacement dose(s) after cardiopulmonary bypass

Subjects will receive MEDI8897 for Dose 1 and placebo for Doses 2 through 5:

1 Season 1

(a) Infants < 5 kg body weight at time of dosing:

- Dose 1: A dose of 50 mg (ie, 0.5 mL) MEDI8897 will be obtained by withdrawing the entire contents of 1 investigational vial with an appropriately sized syringe, and administered as one single (ie, 0.5 mL) injection
- Doses 2 through 5: A corresponding volume (0.5 mL) of saline will be obtained, and administered as one single (ie, 0.5 mL) injection

(b) Infants ≥ 5 kg body weight at time of dosing:

- Dose 1: A dose of 100 mg (ie, 1.0 mL) MEDI8897 will be obtained by withdrawing the entire contents of 2 investigational vials
- Doses 2 through 5: A corresponding volume (1.0 mL) of saline will be administered
- To maintain the blind:
 - If the weight is ≥ 5 kg to < 6.7 kg then the dose should be administered as one single (ie, 1.0 mL) injection
 - If the weight is ≥ 6.7 kg, then the volume of MEDI8897 or saline should be divided equally into 2 syringes

2 Season 2

- Dose 1: A dose of 200 mg (ie, 2.0 mL) MEDI8897 will be obtained by withdrawing the entire contents of 4 investigational vials
- Doses 2 through 5: A corresponding volume (2.0 mL) of saline will be administered
- To maintain the blind:
 - If the weight is < 13.4 kg, then the dose should be administered as two 1.0 mL injections (ie, 1.0 mL per injection)
 - If the weight is ≥ 13.4 kg, then the volume of MEDI8897 or saline should be divided equally into 3 syringes

3 Replacement dose(s) after cardiopulmonary bypass

Season 1

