(a) Cardiopulmonary bypass < 90 days post first dose of MEDI8897 (or most recent replacement dose if previous cardiopulmonary bypass) for infants < 5 kg:

- Replacement dose: A dose of 50 mg (ie, 0.5 mL) MEDI8897 will be obtained by withdrawing the entire contents of 1 investigational vial with an appropriately sized syringe, and administered as one single (ie, 0.5 mL) injection

- (b) Cardiopulmonary bypass < 90 days post first dose of MEDI8897 (or most recent replacement dose if previous cardiopulmonary bypass) for infants ≥ 5 kg:
 - Replacement dose: A dose of 100 mg (ie, 1.0 mL) MEDI8897 will be obtained by withdrawing the entire contents of 2 investigational vials
 - To maintain the blind:
 - If the weight is ≥ 5 kg to < 6.7 kg then the dose should be administered as one single (ie, 1.0 mL) injection
 - If the weight is ≥ 6.7 kg, then the volume of MEDI8897 should be divided equally into 2 syringes
- (c) Cardiopulmonary bypass ≥ 90 days post first dose (or most recent replacement dose if previous cardiopulmonary bypass) for all weights:
 - Replacement dose: A dose of 50 mg (ie, 0.5 mL) MEDI8897 will be obtained by withdrawing the entire contents of 1 investigational vial with an appropriately sized syringe, and administered as one single (ie, 0.5 mL) injection

Season 2

- (a) Cardiopulmonary bypass < 90 days post first dose:
 - Replacement dose: A dose of 200 mg (ie, 2.0 mL) MEDI8897 will be obtained by withdrawing the entire contents of 4 investigational vials
 - To maintain the blind:
 - If the weight is < 13.4 kg, then the dose should be administered as two 1.0 mL injections (ie, 1.0 mL per injection)
 - If the weight is ≥ 13.4 kg, then the volume of MEDI8897 should be divided equally into 3 syringes
 - (b) Cardiopulmonary bypass ≥ 90 days post first dose (or most recent replacement dose if previous cardiopulmonary bypass):
 - Replacement dose: A dose of 100 mg (ie, 1.0 mL) MEDI8897 will be obtained by withdrawing the entire contents of 2 investigational vials
 - To maintain the blind:
 - If the weight is ≥ 5 kg to < 6.7 kg then the dose should be administered as one single (ie, 1.0 mL) injection
 - If the weight is ≥ 6.7 kg, then the volume of MEDI8897 should be divided equally into 2 syringes
- 4 Switch the needle prior to administration

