 - 5 MEDI8897 or placebo (saline) should be administered in the anterolateral aspect of the thigh according to standard practice procedures for IM injections. The injection should be given using standard aseptic technique. When possible, injection sites for subsequent injections should use alternating sites (eg, right then left thigh). The maximum volume to be administered with each injection is 1.0 mL
 - 6 MEDI8897 or placebo (saline) should be administered using the appropriate size needle ranging from 22 to 25 gauge and 5/8 to 1.0 inches based on muscle size and weight of the subject

Palivizumab group: Season 1 and Season 2, including replacement dose(s) after cardiopulmonary bypass

- 1 A dose of 15 mg/kg palivizumab will be obtained by withdrawing the calculated volume of drug to the nearest 0.01 mL as described below:

The dose of palivizumab will be calculated based on the subject's weight (to the nearest 0.01 kg) using the following formula:

$$\text{Dose (mL)} = [\text{subject weight (kg)} \times \text{dose level (15 mg/kg)}] \div \text{palivizumab concentration (100 mg/mL)}$$

The corresponding volume of palivizumab should be rounded to the nearest 0.01 mL.

Examples:

A patient who weighs 4.90 kg at the time of injection receives 0.74 mL of study drug (4.90 kg x 15 mg/kg) ÷ 100 mg/mL = 0.735 mL (rounded to 0.74 mL)

A patient who weighs 3.70 kg at the time of injection receives 0.56 mL of study drug (3.70 kg x 15 mg/kg) ÷ 100 mg/mL = 0.555 mL (rounded to 0.56 mL)

- 2 Switch the needle prior to administration
- 3 Palivizumab should be administered in the anterolateral aspect of the thigh according to standard practice procedures for IM injections. The injection should be given using standard aseptic technique. When possible, injection sites for subsequent injections should use alternating sites (eg, right then left thigh). The maximum volume to be administered with each injection is 1 mL
- 4 Palivizumab should be administered using the appropriate size needle ranging from 22 to 25 gauge and 5/8 to 1.0 inches based on muscle size and weight of the subject

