4.6.3 Methods for Unblinding

4.6.3.1 Unblinding in the Event of a Medical Emergency

In the event of a medical emergency, the investigator may unblind an individual subject's investigational product allocation. Instructions for unblinding an individual subject's study drug allocation are contained in the IWRS manual. In general, unblinding should only occur if

management of the medical emergency would be different based on the subject having received study drug. In the majority of cases, the management of a medical emergency would be the same whether or not study drug was received by the subject. If this was the case, the study drug allocation should not be unblinded. In the event there is unblinding, the investigator should promptly document and explain to MedImmune the reason for any premature unblinding.

MedImmune retains the right to unblind the treatment allocation for SAEs that are unexpected and are suspected to be causally related to a study drug and that potentially require expedited reporting to regulatory authorities.

If a subject's study drug allocation is unblinded to the blinded staff or blinded MedImmune/contract research organization study team, the subject should be discontinued from study drug.

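### Two late replacement-dose rules in Protocol Section 4.5.1.2 omit the section's own blinding splits, so infants of the same weight can get different numbers of injections by arm

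*Protocol*

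**What the plan says.** Section 4.5.1.2 sets palivizumab volume as weight times 15 mg/kg divided by 100 mg/mL. "The corresponding volume of palivizumab should be rounded to the nearest 0.01 mL", and "The maximum volume to be administered with each injection is 1 mL". Section 3.1.2.3 uses the same weight-based dose for replacements, whatever the time since Dose 1: "Subjects will receive a 15 mg/kg palivizumab IM replacement dose".

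For the MEDI8897 arm, Section 4.5.1.2 gives fixed volumes and, as a stated blinding measure, says how many syringes to use by weight:

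- **Season 1, scheduled.** Below 5 kg: 0.5 mL in one injection. From 5 kg to below 6.7 kg: 1.0 mL in one. From 6.7 kg: 1.0 mL in two. For Doses 2-5 below 5 kg: "A corresponding volume (0.5 mL) of saline will be obtained, and administered as one single (ie, 0.5 mL) injection".
- **Season 1 replacement before 90 days.** The same steps.
- **Season 1 replacement at 90 days or more.** One 0.5 mL injection, with the scope "or most recent replacement dose if previous cardiopulmonary bypass) for all weights" and no blinding split.
- **Season 2, scheduled, and replacement before 90 days.** 2.0 mL: "If the weight is < 13.4 kg, then the dose should be administered as two 1.0 mL injections"; from 13.4 kg, three syringes.
- **Season 2 replacement at 90 days or more.** 1.0 mL: one injection from 5 kg to below 6.7 kg, two from 6.7 kg, and no further step.

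Section 4.6.2 has syringe barrels covered. It also requires each site to keep a written plan covering who is blinded and how study drug is given so that the blind holds.

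**The concern.** By tying syringe number to weight, the protocol itself treats the injection count as something that could disclose the arm. A rule that omits the split leaves that route open. A parent, or a blinded staff member who learns the count, could infer the arm from it.

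What is at stake is the safety comparison. The primary endpoint is the occurrence of adverse events (Section 2.1), and the investigator judges the severity of each event and its relationship to study drug (Section 5.5). The leak could also carry forward: under Section 4.6.1, CLD/CHD infants randomized to MEDI8897 in Season 1 stay on it in Season 2, so a correct inference in Season 1 also gives the Season 2 arm.

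**Working it through.** **Inputs.** All come from Protocol Section 4.5.1.2: 15 mg/kg, 100 mg/mL, rounding to 0.01 mL, and a 1 mL maximum per injection.

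**Formulas.** Palivizumab volume = weight × 15 / 100 = 0.15 mL/kg, rounded half-up to 0.01 mL. Minimum number of injections = volume / 1 mL, rounded up.

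**Check against the protocol's examples.** 4.90 × 0.15 = 0.735, which rounds to 0.74 mL, as in "A patient who weighs 4.90 kg at the time of injection receives 0.74 mL of study drug". 3.70 × 0.15 = 0.555, which rounds to 0.56 mL, also as printed.

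**Reproducing the thresholds.**

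- 6.69 kg: 1.0035, rounds to 1.00 mL, one injection. 6.70 kg: 1.005, rounds to 1.01 mL, two injections. The stated 6.7 kg is reproduced.
- 13.36 kg: 2.004, rounds to 2.00 mL, two injections. 13.37 kg: 2.0055, rounds to 2.01 mL, three injections. The stated 13.4 kg is reproduced to within 0.03 kg.

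**Injections at the same weight, MEDI8897 arm vs palivizumab arm.** Season 1 was checked to 12.99 kg. Season 2 was checked from 5 to 18 kg.

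| Dose | Below 6.7 kg | 6.70-13.36 kg | From 13.4 kg |
|---|---|---|---|
| Season 1 scheduled; replacement before 90 days | 1 vs 1 | 2 vs 2 | not checked |
| Season 1 replacement, 90 days or more | 1 vs 1 | **1 vs 2** | not checked |
| Season 2 scheduled; replacement before 90 days | **2 vs 1** | 2 vs 2 | 3 vs 3 |
| Season 2 replacement, 90 days or more | 1 vs 1 | 2 vs 2 | **2 vs 3** |

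The first row assumes that weight is re-read at each visit. At 13.37-13.39 kg both Season 2 rows give 2 vs 3. For the scheduled-dose row this is only a rounding gap.

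**Which mismatches are forced.** The 1 vs 2 and 2 vs 3 cells follow from the text, because palivizumab exceeds the per-injection maximum. For example, 7 kg gives 1.05 mL and 13.4 kg gives 2.01 mL. The 2 vs 1 cell is not forced: it assumes that palivizumab of 1 mL or less goes into one syringe. The protocol does not say so, although its Season 1 6.7 kg step rests on the same idea.

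**Who can fall in these cells.** Replacement doses apply only to the CLD/CHD cohort (about 300 of 900 planned), for bypass surgery after Dose 1 and before Dose 5. Ninety days after Dose 1 is Day 91 and Dose 5 is Day 121, so with no earlier replacement the window is about 30 days. The weights are plausible: Section 4.5.1.2 writes a rule for Season 1 infants of 6.7 kg and above, and Section 3.2.1 expects about 8.5 to 15 kg in Season 2. The 2 vs 1 cell lies below that range, but SAP Section 3.7.5 mentions a small number of infants under 7 kg on Season 2 Day 1.

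**Season 1 Doses 2-5.** Suppose the 0.5 mL saline rule follows weight at Dose 1. An infant just under 5 kg who gains a little over 1.7 kg (6.7 − 5.0) before a later dose would then get one saline injection where palivizumab needs two. If weight is read again at that visit, the infant falls under the 6.7 kg step and the counts agree.

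**The case against.** The case for leaving the text alone has five parts.

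- **Most cells agree.** This stands. A reader might infer that replacement doses in general, or scheduled doses in general, disclose the arm. The table does not support that: Season 1 replacements before 90 days match at every weight checked, and so do Season 2 scheduled doses from 6.7 kg, apart from the rounding gap.
- **The late replacements are rare.** This also stands. They need bypass surgery in a narrow window and a weight above the step.
- **Growth during Season 1.** A reader might take it as fact that infants who start under 5 kg lose the match by Dose 5. The Season 1 rules classify infants by weight when dosed, and weight is recorded at every dosing visit, so the matching reading is open. The reference to a corresponding saline volume leaves it unsettled. The documents give no weight-gain figure, so this is an ambiguity and not a demonstrated mismatch.
- **Site blinding plans.** Section 4.6.2 requires one, and it could keep the count from those who must stay blinded. The documents do not say that it does, and the parent must stay blinded too. The finding is therefore a risk and not a shown unblinding.
- **Stopping study drug.** Section 4.6.3.1 says that after unblinding "the subject should be discontinued from study drug", and a reader might conclude that a mismatched count costs an infant treatment. That sentence concerns an allocation that has actually been unblinded. It does not extend to a guess from the number of injections.

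**Conclusion.** The point holds in a narrow form. Section 4.5.1.2 departs from its own blinding thresholds in two rules: the Season 1 replacement at 90 days or more (1 vs 2 injections from 6.7 kg) and the Season 2 replacement at 90 days or more (2 vs 3 from about 13.4 kg, inside the expected weight range). Both follow from the printed volumes and the 1 mL maximum.

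The Season 2 2 vs 1 count below 6.7 kg is an edge case that rests on single-syringe palivizumab. It would recur at all five scheduled doses while the infant stays under that weight. Season 1 Doses 2-5 need clarification only.

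The number of infants is small and cannot be derived from the documents. That any arm is disclosed also assumes that a blinded person learns the count and knows the rule. The case for acting is that the gap is avoidable and that investigators assess the adverse events.

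**What to change.** Reconcile the injection-count passages in Section 4.5.1.2 with the section's own 6.7 kg and 13.4 kg thresholds and its per-injection maximum, so that infants of the same weight receive the same number of injections in both arms at every dose, replacements included. Clarify which weight the Season 1 rule for Doses 2-5 refers to.

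For Season 2 infants below 6.7 kg, the agreement cannot come from giving the 2.0 mL MEDI8897 or saline volume as one injection, because that would breach the 1.0 mL maximum. The two arms' instructions have to be read together there.

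No dose changes. The cost is wording in the protocol and pharmacy instructions, and possibly one extra syringe for a few infants.

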4.5.1.3 Monitoring of Dose Administration

Subjects will be monitored before and after investigational product administration through assessment of vital signs (temperature, blood pressure, heart rate, and respiratory rate). All vital signs should be obtained within 60 minutes prior to dosing, and at 30 minutes (± 5 minutes) and 60 minutes (± 5 minutes) post dose.

As with any biologic product, allergic reactions to dose administration are possible. Therefore, appropriate drugs and medical equipment to treat acute anaphylactic reactions must be immediately available, and study personnel must be trained to recognize and treat anaphylaxis.

4.5.2 Additional Study Medications

No other study medications are specified for use in this clinical protocol.

4.5.3 Labeling

Labels for the investigational product will be prepared in accordance with Good Manufacturing Practice and local regulatory guidelines. Label text will be translated into local languages, as required.

4.5.4 Storage

Store MEDI8897 and palivizumab at 2°C to 8°C. Placebo (saline) should be stored according to the manufacturer instructions.

4.5.5 Treatment Compliance

Investigational product is administered by study site personnel, who will monitor compliance.

4.5.6 Accountability

The investigator's or site's designated investigational product manager is required to maintain accurate investigational product accountability records. Upon completion of the study, copies of investigational product accountability records will be returned to MedImmune. All unused MEDI8897 and palivizumab will be returned to a MedImmune-authorized depot or disposed of upon authorization by MedImmune.

4.6.2 Methods to Ensure Blinding

This is a double-blind study in which MedImmune will provide sites with MEDI8897 and palivizumab. Sites will use commercially available saline as the placebo. Syringe barrels will be covered by the unblinded investigational product manager. Neither the subject/legal representative nor the investigator or any of the site staff who are involved in the treatment or clinical evaluation of the subjects will be aware of the treatment received (ICH E9). In the event that treatment allocation for a subject becomes known to the investigator or other blinded study staff involved in the management of study subjects, the sponsor must be notified *immediately*. If the treatment allocation for a subject needs to be known to treat an individual subject for an AE, the investigator must notify the sponsor *immediately*. The site will maintain a written plan detailing which staff members are blinded/unblinded and the process of investigational product administration used to maintain the blind.

4.6.3 Methods for Unblinding

4.6.3.1 Unblinding in the Event of a Medical Emergency

In the event of a medical emergency, the investigator may unblind an individual subject's investigational product allocation. Instructions for unblinding an individual subject's study drug allocation are contained in the IWRS manual. In general, unblinding should only occur if

management of the medical emergency would be different based on the subject having received study drug. In the majority of cases, the management of a medical emergency would be the same whether or not study drug was received by the subject. If this was the case, the study drug allocation should not be unblinded. In the event there is unblinding, the investigator should promptly document and explain to MedImmune the reason for any premature unblinding.

MedImmune retains the right to unblind the treatment allocation for SAEs that are unexpected and are suspected to be causally related to a study drug and that potentially require expedited reporting to regulatory authorities.

If a subject's study drug allocation is unblinded to the blinded staff or blinded MedImmune/contract research organization study team, the subject should be discontinued from study drug.

4.7 Restrictions During the Study and Concomitant Treatment(s)

The investigator must be informed as soon as possible about any medication taken from the time of screening until the final study visit. Any concomitant medication(s), including herbal preparations, taken during the study will be recorded in the electronic case report form (eCRF).

4.7.1 Permitted Concomitant Medications

Investigators may prescribe concomitant medications or treatments deemed necessary to provide adequate supportive care including routine vitamins and iron. Specifically, subjects should receive full supportive care during the study, including transfusions of blood and blood products, and treatment with antibiotics, anti-emetics, anti-diarrheals, and analgesics, and other care as deemed appropriate, and in accordance with their institutional guidelines.

4.7.2 Prohibited Concomitant Medications

Use of concomitant medications including over-the-counter medications (except for routine vitamins and iron), herbal supplements, etc from Day 1 through Day 15 post dose is discouraged. Subject's legal representative must be instructed not to administer any medications, including over-the-counter products, without first consulting with the investigator.

4.8 Statistical Evaluation

4.8.1 General Considerations

Tabular summaries will be presented by treatment group. Categorical data will be summarized by the number and percentage of subjects in each category. Continuous variables will be

summarized by descriptive statistics. Additional details of statistical analyses will be described in the statistical analysis plan.

The Intent-to-treat (ITT) Population is defined as all randomized subjects, analyzed according to randomized treatment assignment. All efficacy analyses will be performed on the ITT Population.

The As-treated Population (ATP) is defined as all subjects who receive any investigational product, analyzed according to treatment received. All analyses, with the exception of efficacy, will be performed on the ATP unless otherwise specified.

A primary analysis, Season 2 analysis, and final analysis are planned for the study. The primary analysis will be conducted after all randomized subjects have completed follow-up through the first 5-month RSV season (ie, Season 1 Day 151 visit) and include all available Season 1 safety, efficacy, PK, and ADA data at the time of the data cutoff. Season 2 analysis will be conducted after all the CLD/CHD subjects have completed follow-up through the second 5-month RSV season (ie, Season 2 Day 151 visit) and include all available Season 1 data and Season 2 safety, efficacy, PK, and ADA data at the time of the data cutoff. The final analysis will be conducted when all subjects have completed the last visit of the study and include all data collected in the study.

At the time of the primary analysis, the Season 1 data will be unblinded to the Sponsor/designated clinical research organization associated with the analysis, write-up, and regulatory submission.

To ensure the blinding of Season 2 treatment assignment for CLD/CHD subjects who were randomized to the palivizumab arm in Season 1, any data with potential unblinding risk will be split by Season 1 and Season 2 by the corresponding third party data vendors and when the primary database lock occurs, only unblinding data from Season 1 will be transferred to the Sponsor for analysis.

The site personnel, participants, and the study team members who participate in the advice or decisions involving study subjects and/or day-to-day interactions with the site, will remain blinded until the end of the study to ensure the trial integrity is maintained. Further details will be specified in the unblinding plan prior to database lock for the primary analysis.

